# **10.2 OUTCOME MEASURES**

The primary aims of the trial are to assess whether aspirin can prevent recurrence and prolong survival in individuals who have had radical treatment for cancer. This will be achieved by means of a combined cohort analysis on overall survival including all four cohorts. Allied to this, cohort-specific analyses will allow investigation of the specific effects of aspirin on each tumour type.

Overall survival is a key outcome of interest in Add-Aspirin that will allow an assessment of the overall health benefits of adjuvant aspirin in patients with early stage cancer. However, with the exception of the gastro-oesophageal cohort, using overall survival as the primary outcome in the tumour-specific comparisons would lead to unfeasibly large sample sizes and results emerging many years later in comparison with alternative outcome measures such as disease- or recurrence-free survival. This is because we can anticipate a smaller treatment effect on overall survival, and relatively good cancer-related outcomes in these patient groups, with many patients dying from causes other than cancer in all but the gastro-oesophageal cohort. The additional power afforded by the combined cohort analysis, due to its larger sample size and longer follow-up, will allow an assessment of overall survival across all cohorts.

#### **10.2.1 PRIMARY OUTCOME MEASURES**

For the combined cohort analysis, the primary outcome measure will be time to death from any cause. The cohort specific primary outcome measures are also all time-to-event variables and are defined in table7. Details of outcome assessments are given in section 6.

Соногт	PRIMARY OUTCOME MEASURE	
Cohorts combined	Overall survival (OS)	
	Time from randomisation to death from any cause	
Breast cancer	Invasive disease-free survival (IDFS)	
	Time from randomisation to invasive disease or death from any	
	cause. Invasive disease is defined as:	
	Ipsilateral invasive breast tumour recurrence	
	Regional invasive breast cancer (ipsilateral breast)	
	Distant recurrence	
	Contralateral invasive breast cancer	
	
 
Second primary (non-breast) invasive cancer
 
	
Colorectal cancer	Disease-free survival (DFS)	
	Time from randomisation to disease recurrence (local or distant) or	
	death from any cause.	
Gastro-oesophageal cancer	Overall survival	
	Time from randomisation death from any cause.	
Prostate cancer	Biochemical recurrence-free survival (bRFS)	
	Time from randomisation to PSA failure (as defined in 6.3.1),	
	clinical progression, initiation of salvage treatment or prostate	
	cancer death.	

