# 3.2 BREAST COHORT EXCLUSION CRITERIA

- 1. Metastatic or bilateral breast cancer.
- 2. Current or previous regular use of aspirin (at any dose) or current use of another NSAID for any indication (see appendix I for list of medications not permitted in the trial).
  - Regular aspirin use is defined as taking aspirin more than twice in any given week for more than 4 consecutive weeks
  - Previous regular use of aspirin ≥5 years agois acceptable. Any previous regular aspirin use within the last 5 years should be discussed with the MRC CTU at UCL who will advise on eligibility on a case-by-case basis
  - Current NSAID use is defined as taking any NSAID for more than a week in the preceding month
  - If investigators feel that these definitions may unfairly exclude a participant, this can be discussed with the MRC CTU at UCL and a case by case decision will be made
- 3. A past history of adverse reaction or hypersensitivity to NSAIDs, celecoxib, aspirin or other salicylates or sulphonamides, including asthma, that is exacerbated by use of NSAIDs.
- 4. Current use of anti-coagulants.
- 5. Current or long-term use of oral corticosteroids. The treating physician should make the clinical decision whether a patient has been exposed to long-term therapy.
- 6. Active or previous peptic ulceration or gastrointestinal bleeding within the last year, except where the cause of the bleeding has been surgically removed.
- 7. Active or previous history of inflammatory bowel disease.
- 8. History of moderate or severe renal impairment, with eGFR<45ml/min/1.73m^2.
- 9. Previous invasive or non-invasive malignancy except:
  - a. DCIS where treatment consisted of resection alone.
  - b. Cervical carcinoma in situ where treatment consisted of resection alone.
  - c. Basal cell carcinoma where treatment consisted of resection alone or radiotherapy.
  - d. Superficial bladder carcinoma where treatment consisted of resection alone or with a single installation of intravesical chemotherapy or with BCG treatment.
  - e. Other cancers where the patient has been disease-free for  $\geq$ 15 years.
  - f. Other cancers with very low potential for recurrence can be discussed with MRC CTU at UCL where eligibility will be considered on an individual basis.

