# 6.3 PROCEDURES FOR ASSESSING EFFICACY

Clinical outcome events, as defined in the Statistical Analysis Plan, will be reported on CRFs to be completed by the Investigator or Research Nurse at each follow-up assessment. Disease recurrence and progression will be assessed at follow-up clinic visits by means of imaging, clinical examination and tumour markers (e.g. carcinoembryonic antigen (CEA), prostate-specific antigen (PSA)) in accordance with routine investigations for that tumour site (see Trial Assessment Schedule). In the prostate cohort, biochemical failure is a primary outcome event and should be reported in accordance with the definitions provided in 6.3.1.

Following disease recurrence/progression in the randomisation phase, participants should normally continue to take their trial medication (see section 5.8 for guidance on treatment following

relapse/progression). Providing they are willing, they should continue to be followed up in the trial, regardless of whether they are still receiving trial medication. Follow-up should adhere as far as possible to the planned assessment schedule, but some variation is acceptable where this differs from local protocols for follow-up after relapse.

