# Table 8: Secondary outcome measures

Соногт	SECONDARY OUTCOME MEASURE	
	Thrombotic events	
	Diagnosis of venous thromboembolism	
	Diabetes and associated complications	
	Diagnosis of diabetes or associated complications (including retinopathy,	
	impaired renal function)	
	Second malignancies	
	Diagnosis of a new primary cancer	
	Age-related macular degeneration (AMD)	
	Diagnosis of AMD	
	Cognitive assessment	
	Using the Montreal Cognitive Assessment (MoCA-Blind)	
	Dementia	
	Diagnosis of dementia (of any type), reported by sub-type	
	Functional capacity	
	Using the VES-13 questionnaire	
	Exercise levels	
	Measured using the International Physical Activity Questionnaire (IPAQ)	
	Long-term quality of life/late effects of cancer treatmentMeasured using	
	survivorship questionnaire	
Breast	Breast cancer-specific survival	
	Time from randomisation to breast cancer death	
	Bone metastases-free survival	
	Time from randomisation to development of bone metastasis or death	
	from any cause	
	IDFS-DCIS	
	Defined as for IDFS except that ductal carcinoma in situ (DCIS) (ipsilateral	
	or contralateral) is additionally included as an event 	
Colorectal	Colorectal cancer-specific survival	
	Time from randomisation to colorectal cancer death	
Gastro-oesophageal	Disease-free survival	
	Time from randomisation to disease recurrence or death from any cause	
Prostate	Prostate cancer-specific survival (PCSS)	
	Time from randomisation to prostate cancer death	
	Time to initiation of salvage treatment	
	Time from randomisation to initiation of salvage treatment	
	Bone metastases-free survival	
	Time from randomisation to development of bone metastasis or death	
	from any cause	

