# 10.4.1 BREAST COHORT

In the breast cohort, based on data from recent trials of adjuvant chemotherapy in similar breast cancer cohorts (specifically TACT, BIG 02-98 and GEICAM), as well as results from the recent Indian study of pre-operative progesterone, and additionally considering that a gradual improvement has been observed over time in outcomes for these patients, 5-year IDFS in the control group is expected to be approximately 80%. The number of patients for this cohort is designed to have 90% power at a 5% 2-sided significance level to demonstrate a 4% absolute improvement in this rate at 5 years (corresponding to hazard ratio, HR=0.78).

Assuming proportional hazards, this will require 275 control arm IDFS events (717 events in total) to be observed. Assuming that the cohort takes  $3^{1}/_{2}$  years to recruit, with the analysis taking place 6 years after the last randomisation, and that complete primary outcome data will not be obtainable for 10% of randomised participants by the time of analysis, the anticipated sample size needed to observe this number of events is approximately 3100 randomised participants. We expect to register at least 3450 breast cancer participants for the run-in period to allow for at least 10% not proceeding beyond that stage.

If an effect of aspirin were not observed for the first two years, it is estimated that the power achieved by the logrank test at the time of analysis would be approximately 83% with the proposed sample size. This calculation assumes a hazard ratio of 1 (no effect) over the first two years followed by a hazard ratio of 0.71 thereafter, which yields a mean hazard ratio of approximately 0.78 (the targeted hazard ratio for this cohort) at the time of the primary analysis of the cohort.

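### Breast IDFS counts every second primary non-breast invasive cancer with no basal cell carcinoma exception: an over-inclusive event list that could cost about 1 to 6 points of power

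*Protocol*

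**What the plan says.** Section 10.2.1, Table 7, defines breast IDFS as time from randomisation to invasive disease or death from any cause and lists five kinds of invasive disease. The last is "Second primary (non-breast) invasive cancer". No skin-cancer exception appears there or elsewhere in the protocol.

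The all-cohort secondary outcome of second malignancies in Table 8 is equally broad: "Diagnosis of a new primary cancer".

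The entry criteria do draw a line. Section 3.2, exclusion 9, opens "Previous invasive or non-invasive malignancy except", and one exception is "Basal cell carcinoma where treatment consisted of resection alone or radiotherapy".

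On where events are defined, section 6.3 says "Clinical outcome events, as defined in the Statistical Analysis Plan, will be reported on CRFs". Section 10.2.1, however, presents Table 7 as the definition of the cohort-specific primary outcomes, and section 5.8 sends sites to section 10.2 when assessing recurrence.

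The breast cohort is sized in section 10.4.1 for "90% power at a 5% 2-sided significance level to demonstrate a 4% absolute improvement" ("corresponding to hazard ratio, HR=0.78"), with 275 control-arm events and 717 in total.

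**The concern.** Table 7 handles the in situ boundary with care. The word invasive keeps ductal carcinoma in situ out of IDFS, and Table 8 provides a separate IDFS-DCIS outcome to bring it back in. It draws no such boundary for basal cell carcinoma. A small skin lesion excised in year 2 would therefore end a participant's IDFS follow-up exactly as a distant recurrence would.

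The breast rationale in sections 1.2.3 and 1.3.1 concerns breast cancer incidence, recurrence and death, and does not mention skin cancer. If aspirin leaves these lesions unchanged, each one adds an event that carries no treatment signal. Two consequences follow.

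- The observed hazard ratio moves towards 1.
- Because sections 10.4 and 10.7 set the exact analysis date by control-arm events, such events bring the analysis forward with fewer informative ones behind it.

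What is at stake is power for the breast primary comparison, not its validity.

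**Working it through.** **Inputs from the protocol (sections 10.1 and 10.4.1).**
- "5-year IDFS in the control group is expected to be approximately 80" per cent, giving a control hazard of -ln(0.80)/5 = 0.0446 per year.
- Target hazard ratio 0.78 (ln 0.84 / ln 0.80 = 0.781).
- Two-sided 5% level and 90% power.
- Aspirin arms combined, so 2:1 allocation.
- 3100 participants, 3.5 years of recruitment, 6 further years of follow-up, and 10% without complete outcome data.

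**Reproducing the plan's figure.** Freedman's formula for 2:1 allocation is D = (1.960 + 1.282)² × (1 + 2HR)² / [2(1 - HR)²].
- At HR 0.78, D = 10.507 × 6.5536 / 0.0968 = 711. At the unrounded 0.7814, D = 722. The stated 717 lies between them.
- Power at 717 events is Φ(√(2 × 717) × 0.22 / 2.56 - 1.960) = Φ(1.294) = 90.2%.
- With 930 evaluable controls (3100/3 × 0.9), 1860 on aspirin and follow-up spread uniformly over 6 to 9.5 years, exponential survival gives 271 + 439 = 710 events.

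**Adding skin cancers.** Two assumptions are needed, neither of them in the documents: a rate r of 0.1% to 0.4% per year in every arm, and no effect of aspirin on these lesions. Then
- share of control-arm events = r / (0.0446 + r);
- observed HR = (0.78 × 0.0446 + r) / (0.0446 + r);
- if 275 control events trigger the analysis, total events = 275 + 442 × HR/0.78, where 442 = 717 - 275;
- if the calendar sets the date, total events come from the same accrual model with r added to both hazards.

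| r per year | Share of control events | Observed HR | Control-event trigger: events, power | Calendar: events, power |
|---|---|---|---|---|
| 0 | 0 | 0.780 | 717, 90.2% | 710, 90.0% |
| 0.1% | 2.2% | 0.785 | 720, 88.8% | 726, 89.1% |
| 0.2% | 4.3% | 0.789 | 722, 87.4% | 742, 88.2% |
| 0.4% | 8.2% | 0.798 | 727, 84.3% | 773, 86.4% |

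The loss is 1.4 to 5.9 points under the control-event trigger and 0.9 to 3.6 points at the planned calendar time. In the calendar model, about 19 to 74 skin cancers are counted over all arms, and they pre-empt only about 3 to 11 other first events.

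**Sensitivity.** The table adds skin cancers on top of the 80% IDFS rate. The protocol does not say whether that rate already includes them. If it does, the share is r/0.0446, or 2.2% to 9.0%. At the top of that range the HR is 0.800 and power under the control-event trigger is about 84%, so the picture is much the same.

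In terms of share alone, with the total held at 717 events:
- 2% of control events (about 6 of 275) leaves 88.8% power;
- 5% (about 14) leaves 86.5%;
- 10% (about 28) leaves 82.1%.

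**The case against.** The strongest reply is that section 6.3 refers event definitions to the SAP, which is not available here, so it is not established that basal cell carcinomas will be counted. That stands as a limit on the claim. It does not remove the point: Table 7 already gives an event list, and an SAP that left these lesions out would be narrowing a stated rule, not filling a blank.

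Second, a reader might infer that the endpoint contradicts the entry criteria, or that the protocol regards basal cell carcinoma as prognostically irrelevant. The documents support neither. Eligibility and outcome rules serve different purposes. Exclusion 9 also waives previous DCIS, which is an event in IDFS-DCIS, and other cancers after 15 disease-free years, which no one would drop from IDFS. It never names squamous cell skin cancer, so excluding that needs its own decision.

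Third, the absence of an aspirin effect on these lesions is an assumption. Section 1.2.2 reports reductions in overall cancer incidence with aspirin and gives nothing specific to skin.

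Fourth, a reader might infer bias, or distortion from differing skin-cancer rates between countries. The comparison is randomised and double-blind, and country differences in background rate do not bias it.

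Finally, part of the loss is offset if the analysis keeps to the calendar, because the extra events then add to the total. The table shows that case separately.

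**Conclusion.** The point holds as a question of endpoint wording. Table 7, followed literally, counts a post-randomisation basal cell carcinoma as a breast IDFS event. The definition is broader than the breast rationale calls for.

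Under the assumed rates and no aspirin effect, the hazard ratio moves from 0.78 to about 0.785 to 0.798 and power falls by about 1 to 6 points. At 1% to 2% of control-arm events the loss is under 2 points. It becomes material from about 5%.

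It would be wrong to conclude that the sample size is miscalculated: the 717 events reproduce, and that figure needs no change if these lesions are excluded.

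**What to change.** Amend the last component of breast IDFS in Table 7 so that it excludes basal cell carcinoma of the skin, and state explicitly whether other non-melanoma skin cancer counts. Use the same wording for second malignancies in Table 8 and in the SAP, fixed before unblinding. Tabulate the excluded cancers separately by arm so that nothing is lost.

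The cost is a line in each of two tables plus alignment of the SAP. Section 7.3.1.E already requires a new cancer diagnosis to be reported on an SAE form. The downside is that IDFS events accrue slightly more slowly, so the 275 control-arm events would be reached a little later.

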# Table 7: Primary outcome measures

# **10.2.2** Secondary outcome measures

There are a number of secondary outcome measures that are common to all cohorts, as well as some cohort-specific outcomes, as defined in the table below. Secondary outcomes will be important for providing a comprehensive assessment of the potential health benefits and risks of the treatment. Details of outcome assessment are given in section 6. Secondary outcome measures for each cohort are defined below.

COHORT	SECONDARY OUTCOME MEASURE	
All cohorts	Overall survival	
	Time from randomisation to death from any cause	
	(note that this is the primary outcome for the gastro-oesophageal cohort)	
	Adherence	
	Based on participant-reported compliance with taking tablets.	
	During the run-in period, adherence will additionally be assessed on the	
	basis of returned blister packs and diary cards.	
	There is also a translational sub-study which will assess adherence based	
	on thromboxane $B_2$ levels measured in urine and serum samples (see	
	section 9.1 ).	
	Toxicity	
	Based on CTCAE v4	
	Serious haemorrhage	
	CTCAE (v4) grade 3 or greater	
	Serious vascular events	
	Non-fatal myocardial infarction, non-fatal stroke or vascular deaths (using	
	the definition applied by the Antithrombotics Trialists' collaboration) 	

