# 1.4 ASPIRIN TOXICITY AND RISK-BENEFIT CONSIDERATIONS

The use of aspirin as a primary prevention strategy against cancer has been limited by concerns about toxicity, particularly serious haemorrhage. Previous reports of rates of serious bleeding from clinical trials of anti-platelet agents are often inconsistent. This is likely to be due to the lack of a standardised definition of serious bleeding. In a meta-analysis of six randomised controlled trials of primary cardiovascular prevention (n>95,000, mean age 56 years, 46% male) by the Antithrombotic Trialists Collaboration (ATTC) allocation to aspirin increased the incidence of gastrointestinal haemorrhage or other serious extracranial bleed (usually defined as requiring transfusion or resulting in death) from 0.07% per year to 0.1% per year (HR=1.54, 95% CI 1.30-1.82). The increase was only observed for non-fatal bleeds and there were fewer fatal bleeds in participants allocated aspirin compared with the controls. Haemorrhagic strokes (cranial bleeds) occurred at a rate of 0.04% per year compared with 0.03% in the control group. In these studies, aspirin doses ranged from 75-500mg daily. An earlier meta-analysis of 24 randomised trials (n=66,000) estimated that regular aspirin use (for an average of 28 months) increased the risk of gastrointestinal haemorrhage from 1.4% to 2.5% (odds ratio, OR=1.68, 95% CI 1.51-1.88).78 A systematic review by the U.S Preventative Services Task force estimates an additional 1.39 (0.70 to 2.28) GI bleeding events and 0.32 (0.05 to 0.82) for haemorrhagic stroke events per 1000 person-years of aspirin exposure. A number of measures are known to reduce the risk of serious adverse events for those receiving aspirin and these will be recommended in the trial. They include exclusion of patients with a high risk of complications (such as those with a previous ulcer or gastrointestinal bleed); careful management and treatment of symptoms such as dyspepsia; blood pressure monitoring; avoidance of concomitant non-steroidal anti-inflammatory drug (NSAID) use; and a low-dose option for elderly participants. H.pylori testing and eradication will also be carried out and proton pump inhibitors (PPI) will be used where appropriate.

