# 5.4.1.A Blood and lymphatic system disorders

# Rare to very rare:

- Serious bleeding, such as cerebral bleeding, especially in patients with uncontrolled hypertension and/or concomitant treatment with anticoagulants, which in isolated cases may be potentially life-threatening, have been reported.
- Bleeding, e.g. nosebleeds, bleeding gums, cutaneous bleeding, menorrhagia or urogenital bleeding, possibly with prolongation of the bleeding time. This effect can persist for 4 to 8 days after use.

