# 6.2 PROCEDURES FOR ASSESSING SUITABILITY FOR RANDOMISATION FOLLOWING THE RUN-IN PERIOD

Assessments at the end of the run-in period will focus on treatment adherence and toxicity in order to determine the participant's suitability for randomisation into the trial. Participants will be provided with a diary card to complete during the run-in treatment period. They will be asked to bring this, along with their used blister packs, to their subsequent visit and these will be used to assess adherence. Toxicity will be assessed and documented using CTCAE v4 as for all other follow-up visits. Other assessments at this time include a blood test, blood pressure and an update on usage of concomitant medications, all of which will be assessed as described in section 6.4 for other follow-up visits.

The run-in period should be 7-9 weeks long. Participants will be suitable for randomisation if they have taken at least 80% of their run-in treatment (6 or 7 tablets per week) and have not experienced any aspirin-related severe toxicity (defined as ≥grade 3 CTCAE v4), nor significant gastrointestinal bleeding (grade 3 or 4), active gastrointestinal ulceration, new cases or worsening tinnitus (grade 2 or above), intracranial bleeding or hypersensitivity to aspirin. The Investigator is responsible for the final decision as to whether participants are suitable to be randomised but the Trial Management Group will be available for discussion via the Trial Manager if there are concerns or uncertainties.

The run-in period can be extended where the Investigator decides there is a valid reason for inadequate adherence (e.g. unforeseen social circumstances), or the cause of inadequate adherence is temporary (e.g. reversible dyspepsia, see section 5.4.3.A). Additionally this may apply to patients who may be eligible for CAPP3 and are awaiting results of genetic testing. Where offered, the run-in period would normally be extended by 4 or 8 weeks after which adherence and toxicity would be reassessed in the same way. All extensions to the run-in period must be pre-approved by MRC CTU at UCL via the Trial Managers and only one extension for a maximum of 8 weeks is permitted per participant.

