# APPENDIX II – COMMON TOXICITY CRITERIA

The following table details the grading and definitions of some of the known side-effects and should be used when reporting SAEs and describing toxicities. For the complete list of toxicities, please refer to CTCAE v4.

		GRADE								
Adverse Event	1	2	3	4	5					
Gastro-oesophageal reflux	Mild symptoms; intervention	Moderate symptoms; medical	Severe symptoms; surgical	-	-					
disease	not included	intervention indicated	intervention indicated							
Definition: A disorder charac	terised by reflux of the gastric and	d/or duodenal contents into the c	listal oesophagus. It is chronic in na	ature and usually caused by ir	competence of th					
lower oesophageal sphincte	r, and may result in injury to the o	esophageal mucosal. Symptoms i	nclude heartburn and acid indigest	ion.						
Lower gastrointestinal	Mild; intervention not	Moderate symptoms; medical	Transfusion, radiologic,	Life-threatening	Death					
haemorrhage	indicated	intervention or minor	endoscopic, or elective	consequences; urgent						
		cauterisation indicated	operative intervention	intervention indicated						
			indicated							
Definition: A disorder charac	terised by bleeding from the lowe	r gastrointestinal tract (small inte	estine, large intestine and anus).							
Upper gastrointestinal	Mild; intervention not	Moderate symptoms; medical	Transfusion, radiologic,	Life-threatening	Death					
haemorrhage	indicated	intervention or minor	endoscopic, or elective	consequences; urgent						
-		cauterisation indicated	operative intervention	intervention indicated						
			indicated							
Definition: A disorder charac	terised by bleeding from the uppe	er gastrointestinal tract (oral cavit	y, pharynx, oesophagus and stoma	ich).						
Tinnitus	Mild symptoms; intervention	Moderate symptoms; limiting	Severe symptoms; limiting self	-	-					
	not indicated	instrumental ADL	care ADL							
Definition: A disorder charac	terised by noise in the ears, such a	as ringing, buzzing, roaring or clic	king.	•	.					
Intracranial haemorrhage	Asymptomatic; clinical or	Moderate symptoms; medical	Ventriculostomy, ICP	Life-threatening	Death					
-	diagnostic observations only;	intervention indicated	monitoring, intraventricular	consequences; urgent						
	intervention not required		thrombolysis, or operative	intervention indicated						
			intervention indicated							
Definition: A disorder charac	terised by bleeding from the cran	ium.								

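### The grade 3 threshold for serious haemorrhage in Table 8 leaves out symptomatic grade 2 intracranial bleeds, although the protocol's run-in and stopping rules put no grade limit on intracranial bleeding

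*Protocol*

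**What the plan says.** Table 8 (section 10.2.2) lists serious haemorrhage as a secondary outcome for all cohorts and defines it only as "CTCAE (v4) grade 3 or greater", with no exception by site.

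Appendix II supplies the grades. For intracranial haemorrhage:
- grade 1 is an asymptomatic finding;
- grade 2 is moderate symptoms with medical intervention indicated;
- grade 3 begins with "Ventriculostomy, ICP" monitoring and goes on to intraventricular thrombolysis or an operation being indicated;
- grade 4 is life-threatening;
- grade 5 is death.

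For upper and lower gastrointestinal haemorrhage, grade 3 begins with "Transfusion, radiologic" or endoscopic intervention.

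Other sections handle intracranial bleeding without a grade. The run-in criteria in section 6.2 limit gastrointestinal bleeding to grade 3 or 4, then list "new cases or worsening tinnitus (grade 2 or above), intracranial bleeding or hypersensitivity to aspirin". Sections 5.1 and 5.4.3.C follow the same pattern. Section 5.4.1.A gives its example as "Serious bleeding, such as cerebral bleeding, especially in patients with uncontrolled hypertension". The risk-benefit case in section 1.4 cites cranial bleeds beside serious extracranial bleeds: "Haemorrhagic strokes (cranial bleeds) occurred at a rate of 0.04% per year compared with 0.03% in the control group".

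Serious haemorrhage is the harm singled out in the dose comparison (section 10.8.2). It is also one of the outcomes named for the pooled long-term analysis (section 10.7).

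**The concern.** A uniform CTCAE cut is not uniform in clinical meaning. For intracranial haemorrhage, the step from grade 2 to grade 3 depends on whether a neurosurgical or similar procedure is indicated. A symptomatic, medically managed brain bleed therefore falls below the line, while a transfused gastrointestinal bleed falls above it. The same brain bleed would end trial medication permanently under section 5.4.3.C, yet it would be absent from the outcome that carries the bleeding harm.

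If that bleed is a non-fatal haemorrhagic stroke, Table 8 counts it under serious vascular events. There it is pooled with myocardial infarction and other strokes, which aspirin may prevent. Part of the bleeding excess then offsets apparent vascular benefit instead of showing as bleeding. Section 1.4 itself attributes inconsistent published bleeding rates to the absence of a standard definition, and the rates it cites carry no procedure-based threshold for cranial bleeds. The Table 8 count will not be directly comparable with them.

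**Working it through.** **Definition check**

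| Event | Appendix II grade | Counted in Table 8? | Grade limit in sections 5.1, 5.4.3.C and 6.2? |
|---|---|---|---|
| GI bleed, transfusion indicated | 3 | Yes | Yes, grade 3 or 4 |
| Intracranial bleed, asymptomatic | 1 | No | None |
| Intracranial bleed, moderate symptoms, medical treatment indicated | 2 | No | None |
| Intracranial bleed, grade 3 procedure indicated | 3 | Yes | None |
| Intracranial bleed, life-threatening or fatal | 4 or 5 | Yes | None |

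The rows in conflict are the two uncounted ones. The important one is grade 2, because it is symptomatic.

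**Size**

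The protocol states no expected count or power for this outcome, so there is no figure to reproduce. What follows is illustrative.

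Inputs:
- 9,920 randomised (section 3.9).
- Aspirin to placebo 2:1 overall (section 10.1).
- 5 years of treatment (section 5.2), no attrition assumed.
- Extracranial serious bleeds 0.10% a year on aspirin and 0.07% on control; haemorrhagic strokes 0.04% and 0.03% (section 1.4).

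Person-years:
- Aspirin: 9,920 × 2/3 × 5 = 33,067.
- Placebo: 9,920 × 1/3 × 5 = 16,533.

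Expected events:
- Extracranial: 33,067 × 0.0010 = 33.1 and 16,533 × 0.0007 = 11.6; total 44.6.
- Intracranial: 33,067 × 0.0004 = 13.2 and 16,533 × 0.0003 = 5.0; total 18.2.
- All: 44.6 + 18.2 = 62.8. Intracranial share 18.2 / 62.8 = 29%.

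Let *f* be the share of intracranial bleeds that are grade 1 or 2. The documents do not give it. Events not counted = 18.2 × *f*. Section 1.4 also cites excesses of 1.39 gastrointestinal bleeds and 0.32 haemorrhagic strokes per 1,000 person-years of aspirin, so the measured excess would be 1.39 + 0.32 × (1 − *f*), against 1.71 in full.

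| *f* (assumed) | Events not counted | % of 62.8 | Excess per 1,000 person-years |
|---|---|---|---|
| 10% | 1.8 | 2.9% | 1.68 |
| 25% | 4.5 | 7.2% | 1.63 |
| 50% | 9.1 | 14.5% | 1.55 |
| 75% | 13.6 | 21.7% | 1.47 |

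The effect is on the absolute scale. If *f* is the same in both arms, the rate ratio hardly moves: (0.10 + 0.04) / (0.07 + 0.03) = 1.40 with every intracranial bleed counted, and (0.10 + 0.01) / (0.07 + 0.0075) = 1.42 at *f* = 75%.

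**The case against.** The strongest reply has four parts.

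1. **The worst bleeds are counted.** A reader might infer that the threshold misses the gravest aspirin harm, or every intracranial bleed managed without a procedure. Appendix II does not support that. Grades 4 and 5 count, a fatal bleed counts whatever was done, and grading turns on what is indicated, not on what was performed. This part stands.

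2. **Nothing is lost from the data.** A reader might also infer that a grade 2 bleed would show up only as a vascular event. That is not so. The toxicity row of Table 8 has no grade floor. A bleed leading to admission meets the definition of a serious adverse event in Table 5. Stopping treatment for toxicity requires a Notable Event form (sections 6.9 and 7.2.2). The dose comparison also weighs other secondary outcomes beside haemorrhage. This stands too. The dispute is about which outcome counts the event.

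3. **The sections serve different purposes.** Sections 5.1, 5.4.3.C and 6.2 are rules for stopping treatment or not randomising, and the list in 5.4.3.C also contains grade 2 tinnitus. Section 5.4.1 takes its list from the product label. No sentence says that an intracranial bleed of any grade is serious. This is fair and makes the point one of alignment rather than error. It does not explain why gastrointestinal bleeding carries a grade limit in those rules and intracranial bleeding does not.

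4. **The detail may belong to the analysis plan.** Section 6.3 refers event definitions there. But Table 8 itself fixes the threshold, so the definition is open to comment as it stands.

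**Conclusion.** The point holds in a limited form. Table 8 omits non-fatal, non-life-threatening, symptomatic intracranial haemorrhage for which no grade 3 procedure is indicated. This sits badly with the protocol's own ungraded treatment of intracranial bleeding, and the direction is an undercount of the outcome named as the main harm.

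Intracranial bleeds are about 29% of expected serious bleeds, roughly 18 of 63. That rests on the section 1.4 rates, which come from primary cardiovascular prevention trials with a mean age of 56, and on 5 years without attrition. The uncounted number is about 2 to 14 if 10% to 75% of intracranial bleeds are grade 1 or 2; that range is assumed and the documents do not narrow it. Because it covers grades 1 and 2 together, the symptomatic part is no larger.

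A reader might go on to conclude that the harm of 300 mg against 100 mg is understated. The documents give no intracranial rate by dose, and section 1.5 discusses dose-related toxicity only for the gastrointestinal tract, so no effect on the dose comparison can be quantified. No stated figure in the protocol is wrong. This is a worthwhile improvement to an outcome definition, not a flaw that threatens the trial.

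**What to change.** In Table 8, and in the analysis plan to match, define serious haemorrhage as CTCAE v4 grade 3 or greater at any site, or symptomatic (grade 2 or greater) intracranial haemorrhage. Report intracranial haemorrhage of any grade as a separate component by arm. Keep the plain grade 3 or greater count as a sensitivity analysis.

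Extending the definition to asymptomatic grade 1 findings would go too far, since it would label an observation-only finding as serious beside transfused bleeds. The separate component makes those visible without doing so.

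The cost is one line. Intracranial bleeds on treatment already lead to discontinuation and a Notable Event form, so little or no new data collection is needed. The treatment rules are not touched. The downside is a slightly higher reported haemorrhage rate and slightly less uniform grading across bleeding sites.
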